4. STUDY POPULATION

4.1 Population (base)

The study population will be 12 patients with type 1 diabetes. The subjects will be recruited from the following clinics: Rijnstate Hospital, Hospital Gelderse Vallei or Slingeland Hospital.

4.2 Inclusion criteria

In order to be eligible to participate in this study, a subject must meet all of the following criteria:

- Diagnosed with type 1 diabetes mellitus;
- Treated with the Inreda AP system for a minimum of 1 month;
- Age between 18 and 75 years;
- Willing and able to sign informed consent.

Since patients are treated with the Inreda AP, the following inclusion criteria will be met:

- Treated with sensor augmented pump (SAP) therapy or CSII for a minimum of 6 months;
- HbA1c <97 mmol/mol;
- BMI <35 kg/m²;
- No use of acetaminophen, as this may influence glucose sensor measurements.

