| UAVG | Dutch Act on Implementation of the General Data Protection Regulation; in Dutch: Uitvoeringswet AVG |
| URA | Ultrarapid acting |
| WMO | Medical Research Involving Human Subjects Act; in Dutch: Wet Medisch-wetenschappelijk Onderzoek met Mensen |

SUMMARY

Rationale: Inreda Diabetic B.V. (Goor, The Netherlands) developed a bihormonal reactive closed loop system to automate glucose regulation (artificial pancreas; AP) in patients with diabetes mellitus. In the current CE-marked AP, Humalog (Eli Lilly) is used as insulin which is a rapid acting insulin lispro. Lyumjev (Eli Lilly) also consists of insulin lispro but is ultra-rapid acting due to the addition of 2 excipients. Using Lyumjev instead of Humalog insulin could therefore result in better glycemic control.

Objective: The main objective is to determine the efficacy of Lyumjev in the Inreda AP system. Secondary objectives are: to assess safety, differences in pharmacodynamics and differences in AP-related outcome measures.

Study design: This study is a multicenter, open-labeled, randomized, cross-over trial.

Study population: The study population will be 12 patients with type 1 diabetes. The patients will be recruited from the following outpatients clinics: Rijnstate Hospital, Hospital Gelderse Vallei or Slingeland Hospital. The patients are already using the Inreda AP system.

Intervention: The intervention entails use of Lyumjev administered by the Inreda AP system. The subjects will be randomized to receive either Lyumjev or Humalog during the first study period of thirty days. After a wash-out period of eight days, the subject will be switched to the alternate treatment according to randomization.

Main study parameters/endpoints: Main parameter to express efficacy is the time above range (>10 mmol/l), which will be compared between Lyumjev and Humalog.

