8.3 Study procedures

The study starts with informing the patients about the study. If patients want to participate the informed consent form will be signed first and thereafter the patients will be screened, which can be performed online or in the CRC. The study will be performed at home and subjects can live according to their own daily routine.

At the start of the first study period the subject will receive the insulin cartridges for the first study period. After the first 30 days, there will be a washout period of 8 days where subjects will use Humalog. After the wash-out period the subjects will receive the second insulin formulation according to randomization. The same procedure as written above will be repeated. During the study conduct there will be four additional visits by the investigator: at the start and end of both the intervention and control period.

If adverse events occur during the study, the subject has to contact the investigator. If desired, an unscheduled visit could take place. If a device deficiency occurs during the study, the subject has to contact the investigator only if this is insulin-related. If there are other technical problems, the patient should follow the regular treatment protocol and contact the customer service of Inreda Diabetic B.V.

During both study periods subjects are asked to keep a Wi-Fi access point with them so researchers can assess the data if necessary. No active real-time monitoring will be performed during the study, the standard monitoring protocol will be complied. This includes monthly portal assessments and assessments at the request of the customer service.

At the start of the study the self-learning algorithm status (on or off) will not be changed. This means that the self-learning algorithm is turned on or off depending on the setting prior to the study.

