5.1.2 Artificial Pancreas dataset

The AP sends data to the AP Portal system every 10 minutes. The following data will be collected in the AP Portal system:

- AP, transmitters and mobile access point identification;
- Sensor glucose concentration;
- Sensor glucose slope;
- Sensor state;
- Insulin and glucagon administrations;
- Physical activity parameter measured by accelerometers;
- Control algorithm state;
- Events registered by the AP (e.g., low and high glucose alarm, calibrations, infusion set occlusion and replacements, sensor replacements).

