5.3 Standard analysis

The distribution of each parameter (primary, secondary and other study parameters) will be assessed with a histogram and/or q-q plot. For the parameters that are being compared with dependent/paired tests, the distribution of the difference between the groups will be assessed. Based on these assessments, the decision for using data transformations and parametric or nonparametric descriptive analysis and statistical testing will be made for each (group of) parameter(s).

Subsequently, carry-over and period effects will be assessed because of the cross-over design of the study. For each parameter that will be compared between open loop and closed loop, the two randomization groups are first compared using two unpaired t-tests or Mann-Whitney U-tests:

- Sum of open loop and closed loop result (carry-over);
- Difference between the open loop and closed loop result (period).

If a significant difference is found in one of these tests, a carry-over/period effect is present. In that case, the results for that parameter of the second study period cannot be used for the analysis (to estimate the treatment effect) and paired testing will not be possible.

For all statistical tests described in this chapter, a p-value ≤ 0.05 is defined to indicate statistical significance. Descriptive analyses will be performed on the subjects presented in 5.3.3.

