8.1 Description of the deviations from the SAP

1. Standard deviation (SD) of the glucose value

- a. Rationale: SD of the glucose value was included as variable because of its added value to indicate glycemic variability.
- b. Detailed description: the SD of the glucose value was added as parameter considering it is a commonly used parameter besides the coefficient of variation and interquartile range of the glucose value to indicate glycemic variability. The SD was calculated for day time, night time and the combination. No data were affected by the addition of this parameter.
- c. Date of decision: May 1, 2023.
- d. People involved in the decision (with signature): [name], [name] and [name].

2. Time below range (TBR) and time above range (TAR)

- a. Rationale: level 1 and level 2 for the TBR and TAR were included in order to report all the important glycemic metrics, following the International Consensus guidelines.
- b. Detailed description: according to the SAP, only the TBR and TAR in total should be calculated (not as separate levels). In addition to the total TBR and TAR, also level 1 and 2 of the TBR and TAR were calculated. These are essential parameters to indicate glycemic control, following the International guidelines on how to report glycemic metrics (Battelino *et al*, Lancet Diabetes Endocrinol (2023)). These metrics were calculated for day time, night time and the combination. These additional parameters had no effect on the data.

Revision	D02	Document number:	SAP
	Document title:	FAST-1	
	Status:	APPROVED	
	TPL 013.D02	This document is uncontrolled when printed	

- c. Date of decision: May 1, 2023.
- d. People involved in decision (with signature): [name], [name] and [name].

3. Exclusion of AP data acquired for five participants

a. Rationale:

A critical procedural error was discovered in the process of data analysis, which led to invalidity of a part of the FCL data. FCL data from the Lyumjev-Humalog sequence (n=5) had to be excluded. Other data from this sequence could still be included (e.g., adverse events). To mention that all FCL data from the Humalog-Lyumjev sequence (n=7) were included.

b. Details on deviation:

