Humalog is used as default insulin in the Inreda AP, and study participants who were randomized to the Humalog-Lyumjev sequence already had their settings optimized for Humalog by the diabetes care team over a long period, considering AP treatment was their regular care at the time. However, in case study participants were randomized to the Lyumjev-Humalog sequence, their settings needed optimization to match with the characteristics of the ultra-rapid insulin Lyumjev. For these participants, the settings of their insulin curve and preinjection were adjusted to take the faster and shorter insulin action into account. These substantial adjustments of the insulin settings during Lyumjev use were not changed back to the Humalog settings that equaled the settings before the start of the study. The Lyumjev-specific Inreda AP settings that were still used after switching back to Humalog affected the glucose regulation of these participants. Therefore, the true impact on glycemic control comparing the insulins within that sequence could not be studied correctly and would have led to invalid outcomes derived from the FCL data. The FCL data obtained in the Lyumjev-Humalog sequence could therefore not be used as valid study data. Only FCL data from the Humalog-Lyumjev sequence were included to determine the outcome parameters (7 of the 12 participants), whereas FCL data from the Lyumjev-Humalog sequence were excluded from further data analysis (5 of 12 participants).

c. Date of decision:

May 4, 2023.

- d. People involved in decision (with signature): [name], [name] and [name].

8.2 Signatures of the people involved in the decisions:

Name (function): [name] (Data specialist)

Signature: 

Name (function): [name] (Lead Clinical Operations)

Signature: 

Name (function): [name] (Clinical project manager)

Signature: 

Revision	D02	Document number:	SAP
	Document title:	FAST-1	
	Status:	APPROVED	
	TPL 013.D02	This document is uncontrolled when printed	

9 Revision History

Rev	Author	Change description	Reviewed by	Approved by	Date
D01	[name]	New document	[name]	[name]	29-08-2022
D02	[name]	Addition of SAP deviations and signatures of people involved	[name]	[name]	01-07-2025

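### With only the Humalog-first sequence analysed, any time trend falls wholly on Lyumjev; pre-study Humalog data that could serve as a baseline are not used

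*Protocol*

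**What the plan says.** The design is a randomised two-sequence crossover: two 30-day periods, each with five training days left out of the analysis, separated by eight days on Humalog (Protocol section 3). SAP 5.3 plans carry-over and period checks in which "the two randomization groups are first compared using two unpaired t-tests or Mann-Whitney U-tests". If either check is significant, the second period's results are not to be used for that parameter.

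SAP 8.1 item 3 reports that settings adapted to Lyumjev stayed in place after the switch back to Humalog. As a result, "FCL data from the Lyumjev-Humalog sequence (n=5) had to be excluded", and "Only FCL data from the Humalog-Lyumjev sequence were included to determine the outcome parameters (7 of the 12 participants". It describes the participants of the retained sequence as people who "already had their settings optimized for Humalog by the diabetes care team over a long period".

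On experience with the artificial pancreas (AP) before the study, Protocol 4.2 asks only for "Treated with the Inreda AP system for a minimum of 1 month". On the insulin used in that time, the Protocol summary says: "In the current CE-marked AP, Humalog (Eli Lilly) is used as insulin". On data flow, SAP 5.1.2 says: "The AP sends data to the AP Portal system every 10 minutes". Of standard monitoring, Protocol 8.3 says: "This includes monthly portal assessments and assessments at the request of the customer service". Neither document plans a pre-study TAR measure, as a baseline or as a check that control was stable at entry.

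**The concern.** With one sequence left, treatment and period are the same variable. If TAR falls over the two months for reasons unrelated to insulin, the whole fall is counted as a Lyumjev effect. The between-sequence checks in SAP 5.3 need both groups, so they cannot be run on the retained closed-loop data.

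The only support offered for stability is the statement that Humalog settings were already well established. It comes with no months of use and no data, and a one-month entry minimum does not ensure it. Some drift is plausible on the documents' own account: Protocol section 1 describes a self-learning algorithm that adapts to the patient, Protocol 8.3 leaves that algorithm on or off as it was before the study, and settings may be tuned in each training period.

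The same gap affects the period-1 comparison to which SAP 5.3 falls back. It is a small between-patient comparison with no baseline, although a correlated one may be available.

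**Working it through.** **Inputs.** Planned TAR 12.8% and 9.675% (difference 3.125 points), SD 3.3 in each condition, correlation 0.70, alpha 0.05, power 0.90, N = 10 (Protocol 4.4, SAP 3). Sequences of 7 and 5 (SAP 8.1 item 3). Periods of 30 + 8 + 30 days with the first five days of each period excluded (Protocol section 3).

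**The plan's own figure.** SD of the paired difference = 3.3 × √(2 × (1 − 0.70)) = 2.556, and 3.125 / 2.556 = 1.2225. A two-sided paired t-test has power 0.893 at n = 9 and 0.929 at n = 10, so the stated 10 is reproduced. With the 7 analysed, power is 0.769.

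**Where the confounding comes from.** Let T be a drug-unrelated fall in TAR from period 1 to period 2. The error in Lyumjev's favour is:

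| Analysis | Error |
|---|---|
| Both sequences, 6 and 6 | 0 |
| Both sequences, 7 and 5, unadjusted mean | (7T − 5T)/12 = T/6 |
| Both sequences, 7 and 5, period-adjusted | 0 |
| Humalog-Lyumjev only, n = 7 | T |

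**Size under assumed drift.** The analysed windows are days 6–30 (centre 18) and days 44–68 (centre 56), 38 days apart. Drift per 30 days is multiplied by 38/30 = 1.27.

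| Assumed drift per 30 days | T (points) | Share of 3.125 |
|---|---|---|
| 0.5 | 0.63 | 20% |
| 1 | 1.27 | 41% |
| 2 | 2.53 | 81% |

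With no drug effect and n = 7, a two-sided 0.05 test of zero difference favours Lyumjev with probability 0.025 at T = 0, 0.064 at 0.5, 0.14 at 1.0, 0.26 at 1.5 and 0.41 at 2.0.

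**Pre-study data as a stability check (n = 7).** The last 25 days before day 1 are centred on day −12, which is 30 days before day 18. The 95% half-width for period-1 minus pre-study Humalog TAR is 2.447 × 2.556 / √7 = 2.36 points, or 2.36 × 38/30 = 2.99 when scaled to the 38-day gap. That is wider than all three values of T. If the correlation were 0.50 or 0.80 in place of 0.70, the 30-day half-width would be 3.05 or 1.93.

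**Pre-study data to remove a linear trend (n = 7).** The weights on pre-study, Humalog and Lyumjev are 1.267, −2.267 and 1. The SD is 3.3 × √(0.30 × 7.74) = 5.03. Power for 3.125 points is 0.28, and about 30 patients would be needed for 0.90.

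**Pre-study data as covariate in period 1 (5 v 7).** Unadjusted SE = 3.3 × √(1/5 + 1/7) = 1.93. With ANCOVA the variance is multiplied by (1 − r²) and, because the slope is estimated from 12 patients, by about 1 + 1/(12 − 4) = 1.125.

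| Assumed r | SE |
|---|---|
| 0.30 | 1.96 |
| 0.50 | 1.77 |
| 0.70 | 1.46 |
| 0.80 | 1.23 |

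The break-even is r² = 1 − 1/1.125 = 0.111, so r is about 0.33. At r = 0.70 the SE falls by about 24%.

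**The case against.** Several stronger readings are tempting, and the documents do not support them.

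- A reader might blame the entry criterion. A balanced crossover cancels a common trend even with a one-month minimum and no baseline, so the criterion was adequate on this point under the plan as written. The confounding comes from excluding one sequence.
- A reader might see a contradiction between the Protocol's one month and the SAP's account of long optimisation. One month is a floor, and the 7 participants may all have been long-term users.
- A reader might infer that pre-study data are assured. The criterion assures treatment with the AP. It does not assure retrievable data. Protocol 8.3 asks for the Wi-Fi access point only in the study periods, and consent for earlier data is not stated.
- A reader might infer a learning curve. The documents give no estimate of its size or direction.
- A reader might expect pre-study data to separate trend from drug. At n = 7 they cannot, and any correction needs a linearity assumption that cannot be tested here.

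Two further objections carry weight. Under the null hypothesis written in SAP 5.3.1, where Lyumjev must beat Humalog by more than 3.125 points, drifts of 0.63 to 2.53 with no drug effect remain inside the null. They would bias the estimate but would not by themselves establish the stated claim. Also, the 5 v 7 comparison is not currently reported, because item 3 excludes that sequence's period-1 data too. However, the error as described arises after the switch back to Humalog, so it leaves period 1 untouched, and SAP 5.3 itself names the period-1 route as the fallback.

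**Conclusion.** The point holds in a limited form. In the reported n = 7 analysis any time trend is completely confounded with Lyumjev, and the planned checks for period and carry-over effects cannot be run. The claim of well-established Humalog settings is undocumented as to duration, and the entry criterion does not supply one.

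How large the resulting bias is cannot be known from the documents; 0.63 to 2.53 points follows from assumed slopes only. Pre-study Humalog data would not repair the n = 7 comparison. Their useful role is as covariate in a randomised period-1 comparison, where the SE would fall from 1.93 to about 1.46 points. That gain assumes that the planning SD of 3.3 applies and that the planning correlation of 0.70 also holds between the pre-study window and period 1. Below a correlation of about 0.33 there is no gain. A reader might compute a 29% reduction from √(1 − 0.70²) = 0.714, but that treats the slope as known; about 24% is the fairer figure with 12 patients.

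**What to change.** If the data are retrievable and covered by consent, add to SAP 5.1.2 an extraction of AP data for the last 25 days before day 1 for all 12 participants. Then:

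1. In SAP 5.3, specify ANCOVA with pre-study TAR as covariate for any period-1 comparison between sequences.
2. In the Humalog-Lyumjev sequence, report pre-study against period-1 Humalog TAR with its confidence interval, as a descriptive stability check. State that a half-width of about 2.4 points can exclude only a large drift and cannot separate trend from drug.
3. In SAP 8.1 item 3 and the report, describe the n = 7 result as an uncontrolled before-after comparison. List each participant's months on the AP at entry, so that the statement about long optimisation can be judged.

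Label these analyses post hoc, as Protocol section 10 requires for departures from the plan. The cost is one extraction and some SAP wording, with no new visits or patients. The downside is that pre-study portal records may be incomplete and that consent for their use has to be confirmed first. If either fails, item 3 can still be done.

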4.3 Exclusion criteria

A potential subject who meets any of the following criteria will be excluded from participation in this study:

- Impaired awareness of hypoglycemia (score ≥ 4) according to the Gold and/or Clarke questionnaire [3], [4];
- Pregnancy and/or breastfeeding;
- Use of oral antidiabetic agents;
- Insulinoma;
- Hypersensitivity reactions to Lyumjev insulin or any of the excipients;

4.4 Sample size calculation

It is hypothesized that the time above range is reduced in subjects using Lyumjev compared to Humalog. To detect a 3,125% (45 min per day – 15 min per meal) improvement in time spent in hyperglycemia (>10 mmol/l) with a power of 0.90 and alpha of 0.05, 10 subjects are required. To account for drop out of subjects, the sample size will be increased with 2 patients. The sample size calculation has been performed with the program G*Power 3.1.9.4. The percentage time above target range and corresponding standard deviations are based on data from the APPEL 5 study.

The following data were used to calculate sample size:

T-Test: Difference between two dependent means (matched pairs)

Alpha = 0.05

Power = 0.90

Mean 1 = 12.8

Mean 2 = 9.675

SD of mean 1 = 3.3

SD of mean 2 = 3.3

Correlation = 0.70

5. TREATMENT OF SUBJECTS

5.1 Investigational product/treatment

The investigational product is Lyumjev in combination with the AP. Subjects will use their usual diabetes therapy (the AP), but the currently used insulin will be replaced by the investigational product (Lyumjev) for thirty days. The other thirty days of the study will be the control period, where Humalog will be used.

5.2 Use of co-intervention

Patients are not allowed to use acetaminophen, undergo treatment with Magnetic Resonance Imaging, Computed Tomography scan, X-ray or high frequency electrical heat (diathermy), or receive dialysis during the study period. However, these criteria also apply during use of the AP outside of this study.

5.3 Escape medication

Not applicable, as the escape medication does not change from normal AP use.

6. INVESTIGATIONAL PRODUCT

6.1 Name and description of investigational product

The investigational product is Lyumjev (Eli Lilly) administered by the Inreda AP system. The AP is CE marked and Lyumjev is a registered medicinal product.

Lyumjev (Eli Lilly) is classified as an ultra-rapid acting (URA) insulin. Lyumjev has an identical indication compared to Humalog (rapid acting (RA)) and is referred to as insulin lispro-aabc. Although Lyumjev's active substance is identical to Humalog, two additional substances are added which transforms it from rapid acting into ultra-rapid acting insulin. These substances are: treprostinil and citrate, these excipients induce local vasodilation and increase vascular permeability, respectively. This facilitates faster insulin absorption.

6.2 Summary of findings from non-clinical studies

Not applicable.

6.3 Summary of findings from clinical studies

There were four studies conducted to compare the pharmacodynamics of Lyumjev with Humalog [5]–[8]. The results of these studies demonstrate that Lyumjev insulin is non-inferior to Humalog in terms of effectiveness and may improve postprandial glucose control. Interestingly, improved postprandial control is seen only after breakfast, but not after lunch or dinner. Nonetheless, this is promising for AP therapy. Moreover, large studies do not give rise to alarm with regard to side-effects, as similar rates of adverse events are observed in most studies. However, an increase in infusion site reactions was observed and requires attention. So far, large outpatient studies did not include patients on pump therapy. To date, the reported studies have not tested Lyumjev insulin in closed-loop systems. Closed-loop systems are generally able to maintain glycemic control, but postprandial peaks are the final hurdle to achieve normoglycemia in patients using these devices. Using Lyumjev in the AP would potentially further improve glycemic control.

No clinical studies were performed with Lyumjev in combination with the AP system.

